- In Cycle 1, serum for ADA will be collected on Day -1 and predose (± 1 hour) on Days 1, 8, 15, 22, 29, and 36. In Cycles 2 and higher, serum for ADA analysis will be collected predose on Days 1, 15, 22 and 36 (± 2 days). Upon discontinuation from the study, serum for ADA will be collected at EOT (± 2 days), at 14 days post-EOT (± 2 days), and at 28 days post-EOT (± 2 days).
- Radiographic tumor evaluation will be performed by CT/MRI at baseline and at all other disease assessment time points. All studies for the baseline RECIST assessment should be performed within 14 days prior to the first dose of drug. The EOT tumor assessment will not be performed if the subject has had an assessment within the past 30 days.
- ^w The post-treatment fresh tumor biopsy should be performed between 12 and 21 days after first dose of XmAb18087.
- Subjects with a positive ADA at termination will be followed every 28 days (± 3 days) until ADA reverts to baseline or until the next intervening treatment.

Version 1.0 Page 59 of 145

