7.9.1.1. Screening Period (Day -28 to -2)

Subjects will undergo a Screening Visit 2 to 28 days prior to the planned first day of study treatment. Screening assessments are as follows:

- Obtain signed informed consent (Section 17.3)
- Review inclusion and exclusion criteria (Sections 8.1, 8.2, 8.6, and 8.7)
- Medical history
- Demographics
- Physical examination (PE; Section 11.7)
- Collect formalin-fixed paraffin embedded (FFPE) tumor sample or slides for immunohistochemical assessment of MCPyV status (MCC subjects only), tumor cell SSTR2 expression and immune cell expression of proliferation and exhaustion markers
- Perform tumor assessment by CT/magnetic resonance imaging (MRI) per RECIST 1.1 criteria and guidelines (Appendix A) within 14 days prior to the first dose of drug
- Perform NETSPOT gallium 68 dotatate PET/CT if not performed within 3 months prior to enrollment (refer to study manual for details on performing NETSPOT gallium 68 dotatate PET/CT). If the subject has undergone NETSPOT gallium 68 dotatate PET/CT scan within 3 months prior to enrollment and the images and reports of results are available, the scan need not be repeated at baseline; however, a copy of images and the report of scan results must be collected.
- Record any available genetic information on the tumor, including sequencing data
- ECOG performance status (Appendix B)
- Vital signs (Section 11.8)
- Electrocardiogram (ECG) standard 12-lead, supine position (Section 11.6)
- Complete blood count (CBC; Section 11.5)
- Chemistry panel (Section 11.5)
- Coagulation panel (Section 11.5)

Version 1.0 Page 60 of 145

- Screening test for hepatitis B surface antigen (HBsAg) and hepatitis B core antibody (HBcAb; a subject whose HBsAg is negative and HBcAb is positive may be enrolled if a hepatitis B virus [HBV] DNA test is negative and either the subject is treated with potent antiviral therapy or is retested for HBsAg and HBV DNA every month while on study drug treatment).
- Screening tests for human immunodeficiency virus (HIV) and hepatitis C virus (HCV)
- Serum beta human chorionic gonadotropin (β-hCG) pregnancy test for women of childbearing potential or follicle-stimulating hormone (FSH) for postmenopausal women (Section 11.5)
- Urinalysis (Section 11.5)
- Record concomitant medications (Section 9.2)
- Record adverse events (using CTCAE and CRS revised grading system for grading; Section 11.1)

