7.9.3.3. End-of-Treatment Visit

Subjects will have their EOT visit at the end of the last cycle of treatment. If a subject terminates before the end of a cycle, the EOT assessments (Table 7, Schedule of Assessments) will be performed on the day of study termination.

Subjects with a positive ADA at study termination will be followed every 28 days (\pm 3 days), if feasible, until administration of another anticancer therapy, or until ADA levels return to baseline if results are available.

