12. ASSESSMENT OF EFFICACY

Radiographic tumor evaluation will be performed at baseline and at all other disease assessment time points per RECIST 1.1 criteria (Appendix A). If additional clarification or detail is needed, please consult the literature referenced or the Sponsor's Medical Monitor.

The timing for these evaluations will be uniform. Initial evaluation will occur within 14 days (60 days for NETSPOT® gallium 68 dotatate PET/CT) before administration of the first dose of XmAb18087, and follow-up evaluation will be performed on Cycle 1 Day 40 ± 2 days. Reevaluation will be performed after every cycle, as long as the subject continues on study, and at EOT. NETSPOT® gallium 68 dotatate PET/CT scan will be performed and interpreted locally. Copies of images and reports will be collected and sent to Xencor, Inc., for interpretation and archiving. Scans used for RECIST assessments will be performed and interpreted locally. Copies of these images will be collected and stored for potential central assessment at a later date.

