14.7. Efficacy Assessment

The objective of these analyses is to explore the effects of XmAb18087 when administered repeatedly as a single agent across a range of dose levels, in combination with pembrolizumab, and at RD for each Part of the study.

The assessment of antitumor effects of XmAb18087 will be based on response criteria defined in RECIST 1.1 (Appendix A).

The number and percentage of subjects achieving a best overall response of complete response (CR; confirmed and unconfirmed), partial response (PR; confirmed and unconfirmed), stable disease, progressive disease, and not evaluable will be presented.

Overall response rate is defined as subject's best response of PR or better. The number and percent of subjects who achieved ORR will be summarized. Two-sided exact 95% confidence intervals for the ORR will be determined using the binomial distribution. The duration of objective response will be calculated from the time of initial response (PR or better) to the first documentation of relapse (recurrence after CR) or progression (after PR).

The evaluable population defined in Section 14.4 will be used for summary of ORRs and duration of response.

Depending on the completeness of the available follow-up data, an analysis of PFS, measured relative to Day 1, will be performed based on the Kaplan-Meier method. Median time and its 95% confidence interval, as well as the 25th and 75th quartiles with their 95% confidence intervals, will be summarized. Progression will be determined using the criteria described in RECIST 1.1 (Appendix A). The date of progression is defined as the date of progression or death.

Version 1.0 Page 103 of 145

The date of censoring for subjects who end the study without documented progression will correspond to the date the last tumor assessment was performed. Subjects who terminated from study without postbaseline tumor assessment will be censored at Day 1.

Progression-free survival will be presented based on the safety population for the overall study.

The potential antitumor effects of XmAb18087 may also be evaluated in other subgroups of subjects. The specifications for these and other similar analyses will be described in the SAP and supersedes any protocol specifications.

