**Table 1: PFS Censoring Rules**

Situation	Date of Progression or Censoring	Outcome
No baseline tumor assessments	First Dosing visit (Cycle 1 Day 1)	Censored
Documented progression	Earliest of:  Date of radiological assessment showing new lesion(s) (if progression is based on new lesions); or Date of last radiological assessment of measured lesions (if progression is based on increase in sum of target lesions); or Date of last radiological assessment of nontarget lesions (if unequivocal progression occurs based on nontarget lesions)	Progressed
No progression	Date of last radiological assessment	Censored
Treatment discontinuation for undocumented progression	Date of last radiological assessment	Censored
Treatment discontinuation for toxicity or other reason	Date of last radiological assessment	Censored
New anticancer treatment started	Date of last radiological assessment	Censored
Death before first PD assessment	Date of death	Progressed
Death between adequate assessment visits	Date of death	Progressed
Death or progression after missing more than one tumor assessment visit	Date of death or progression	Progressed

PD = progressive disease; PFS = progression-free survival.

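### Read literally, the 30-day waiver of the end-of-treatment scan lets the baseline scan stand in for it, so early Cycle 1 stops may have no post-baseline scan and drop out of PFS as censored at Day 1

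*Protocol*

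**What the plan says.** The footnote to the tumor-assessment row of protocol Table 7 (Section 7.9) sets two rules next to each other. The first concerns baseline: "All studies for the baseline RECIST assessment should be performed within 14 days prior to the first dose of drug." The second is the waiver: "The EOT tumor assessment will not be performed if the subject has had an assessment within the past 30 days." The waiver does not say that the earlier assessment must be post-baseline.

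Other parts of the protocol fix the timing:

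- **Screening (Section 7.9.1.1):** "Subjects will undergo a Screening Visit 2 to 28 days prior to the planned first day of study treatment," so the last screening day is Day -2.
- **First on-treatment scan (Section 12):** "follow-up evaluation will be performed on Cycle 1 Day 40 ± 2 days."
- **EOT scan (Section 12):** "Reevaluation will be performed after every cycle, as long as the subject continues on study, and at EOT." No exception is given.
- **Stops within a cycle (Section 7.9.3.3):** "If a subject terminates before the end of a cycle, the EOT assessments" are done on the day of termination. That section refers back to Table 7 for their content.
- **After EOT (Table 7, Section 7.9.5):** the 14-day and 28-day visits include no tumor scan, and long-term follow-up is remote contact at 6 and 12 months.

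On the analysis side, protocol Section 14.7 presents PFS on the safety population, counts death as an event, and adds: "Subjects who terminated from study without postbaseline tumor assessment will be censored at Day 1." SAP Table 1 handles "Treatment discontinuation for undocumented progression" differently, by censoring at the last radiological assessment. Its Day 1 row covers only a missing baseline assessment. No row covers a subject who has a baseline scan and nothing after it.

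**The concern.** The EOT scan is the only scheduled way to document progression in a subject who stops before Day 40. If a scan taken before the first dose can cancel it, whether an early clinical progression becomes a PFS event depends on how few days separate the stop from the baseline scan. The earliest stops are the ones most likely to lose the scan.

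Those subjects stay in the PFS denominator on paper but contribute no follow-up time. Being censored because of suspected progression is not independent of prognosis, so the Kaplan-Meier curve is pushed upward in the drug's favour. The protocol describes both MCC and SCLC as aggressive or rapidly progressing, so early clinical progression is plausible here.

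**Working it through.** The plan gives no sample size, power or target for PFS, so there is no stated figure to reproduce. The power statements in protocol Section 14.1 concern response rate and are not in question.

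**1. Last stop day on which the baseline scan triggers the waiver.** There is no Day 0, so a scan on Day -b is b days before Day 1, and d + b - 1 days before Day d. The waiver applies when d + b - 1 ≤ 30, that is, when d ≤ 31 - b.

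| Baseline scan | Last waived EOT day | Share of Days 1–37 |
|---|---|---|
| Day -14 (earliest allowed) | 31 - 14 = Day 17 | 17/37 = 46% |
| Day -7 | 31 - 7 = Day 24 | 24/37 = 65% |
| Day -2 (last screening day) | 31 - 2 = Day 29 | 29/37 = 78% |

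Day 37 is the last day before the scan window opens (40 - 2 = Day 38). A stop after the waived range and before Day 38 still requires an EOT scan. That leaves 37 - 17 = 20 days down to 37 - 29 = 8 days.

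**2. What the PFS rules do with a living subject in the waived range who has no other scan.**

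- Protocol Section 14.7: no post-baseline assessment, so censored at Day 1.
- SAP Table 1: censored at the last radiological assessment. Here that is the baseline scan, 2 to 14 days before the first dose from which the SAP measures PFS, so the computed time is negative.

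Either way the subject adds no time at risk.

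**3. Illustrative size.** All of the following are assumptions, not design values:

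- Exponential PFS with a true median of 3 months, borrowed from the protocol's background figure for first-line chemotherapy in MCC.
- A 30.4375-day month.
- The Part A expansion size of 22.
- A share s of the events in the window are clinical progressions in living subjects who stop and are not scanned.

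The monthly hazard is ln 2 / 3 = 0.2310. Days 17 and 29 are 16 and 28 days after Day 1, so:

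- P(event within 16 days) = 1 - exp(-0.2310 × 16/30.4375) = 11.4%
- P(event within 28 days) = 1 - exp(-0.2310 × 28/30.4375) = 19.1%

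If a fraction q = s × P is censored at Day 1, the curve after the window is S(t)/(1 - q), and its median is 3 - ln(1 - q)/0.2310.

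| Window | s | q | Subjects of 22 | Apparent median (months) |
|---|---|---|---|---|
| 16 days | 50% | 5.7% | 1.3 | 3.3 |
| 16 days | 100% | 11.4% | 2.5 | 3.5 |
| 28 days | 50% | 9.6% | 2.1 | 3.4 |
| 28 days | 100% | 19.1% | 4.2 | 3.9 |

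Per subject: with q = 1/22, the shift is -ln(1 - 1/22)/0.2310 = 0.2 months. At s = 0 there is no shift. The documents give no value for s.

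**4. ORR.** The evaluable population requires a complete first cycle, whose last dose is on Day 36, as well as a post-baseline scan. Anyone who stops by Day 29 is excluded whether or not an EOT scan is done.

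**The case against.** The strongest reply is that no sentence says the baseline scan counts, and that Section 12 requires an EOT scan without exception. That is fair as far as it goes: the documents contain an ambiguity and a conflict, not a stated rule that early stoppers go unscanned. But the footnote's wording is unqualified, the sentence just before it calls the baseline scan a RECIST assessment, and elsewhere the authors write postbaseline when they mean it. Two sites could reasonably treat the same subject differently.

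A reader might also infer more than the documents support:

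- **That all Cycle 1 stoppers go unscanned.** Those who stop after Day 17 to Day 29 still have the EOT scan.
- **That fast progressors in general are censored at Day 1.** Deaths are events in both documents. Section 7.4.2 stops treatment on a RECIST assessment of progression, which presupposes a scan. Unscheduled scans are not barred. Some very early stops will be for toxicity, where no progression is hidden. The gap concerns living subjects stopped on clinical grounds without any scan.
- **That later cycles have the same flaw.** There the waiver follows a real post-baseline scan no more than 30 days old, which is shorter than the 42-day cycle. That is a defensible trade-off.
- **That the primary endpoint or this trial's results are distorted.** ORR is unaffected. PFS is secondary, has no hypothesis, and depends under Section 14.7 on how complete follow-up is. SAP Section 5.1 reports 4 subjects and plans listings only.

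**Conclusion.** The point holds for Cycle 1 as a wording defect with a known direction of bias. On the literal reading, the unscanned range runs from Day 1 to between Day 17 and Day 29, or 46% to 78% of the days before the first scan window. For living subjects stopped there for clinical progression with no unscheduled scan, PFS loses events through informative censoring and reads too long. With a 3-month exponential median and half to all of the early events lost, the apparent median would be about 3.3 to 3.9 months. The true shift could be smaller, down to none, because the lost share is unknown.

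The conflict between the footnote and Section 12, and the missing SAP row, need no such assumption. With 4 subjects enrolled and no Kaplan-Meier estimate planned, the present consequence is limited to how an individual listed PFS time would be derived. The value of the correction lies mainly in any reuse of this design.

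**What to change.** 1. Reword the Table 7 footnote so that the EOT tumor assessment may be omitted only if a post-baseline assessment was done within the past 30 days.
2. Reconcile Section 12 with that sentence, so that both places give the same condition.
3. Add a row to SAP Table 1 for subjects with a baseline but no post-baseline assessment: censored at Day 1, unless death occurs, in which case the event is dated at death. This removes the negative time and matches protocol Section 14.7. It is still needed after the first change, because some subjects will miss the EOT scan.

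The cost is one sentence in the footnote, one matching sentence in Section 12, one SAP row, and one EOT scan, already in the schedule, for the few subjects who stop early in Cycle 1. An EOT scan does not guarantee that clinical progression meets RECIST, but it gives those subjects an assessment date and a chance to be counted.

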7.9.1. Pretreatment Evaluations

Only those subjects who meet all inclusion (Sections 8.1 and 8.2) and no exclusion (Sections 8.6 and 8.7) criteria specified may be enrolled into this study. Prior to the initiation of any on-study testing, including screening testing, the subject must have signed the ICF and received a Subject Screening Number (Section 7.6). The pretreatment period lasts for up to 28 days and includes screening evaluations (Day -28 to -2) and baseline assessments (defined as the assessment immediately prior to the first dose).

Prior to administration of XmAb18087, each subject must have completed all screening activities and received approval via the eligibility checklist from the Medical Monitor.

7.9.1.1. Screening Period (Day -28 to -2)

Subjects will undergo a Screening Visit 2 to 28 days prior to the planned first day of study treatment. Screening assessments are as follows:

- Obtain signed informed consent (Section 17.3)
- Review inclusion and exclusion criteria (Sections 8.1, 8.2, 8.6, and 8.7)
- Medical history
- Demographics
- Physical examination (PE; Section 11.7)
- Collect formalin-fixed paraffin embedded (FFPE) tumor sample or slides for immunohistochemical assessment of MCPyV status (MCC subjects only), tumor cell SSTR2 expression and immune cell expression of proliferation and exhaustion markers
- Perform tumor assessment by CT/magnetic resonance imaging (MRI) per RECIST 1.1 criteria and guidelines (Appendix A) within 14 days prior to the first dose of drug
- Perform NETSPOT gallium 68 dotatate PET/CT if not performed within 3 months prior to enrollment (refer to study manual for details on performing NETSPOT gallium 68 dotatate PET/CT). If the subject has undergone NETSPOT gallium 68 dotatate PET/CT scan within 3 months prior to enrollment and the images and reports of results are available, the scan need not be repeated at baseline; however, a copy of images and the report of scan results must be collected.
- Record any available genetic information on the tumor, including sequencing data
- ECOG performance status (Appendix B)
- Vital signs (Section 11.8)
- Electrocardiogram (ECG) standard 12-lead, supine position (Section 11.6)
- Complete blood count (CBC; Section 11.5)
- Chemistry panel (Section 11.5)
- Coagulation panel (Section 11.5)

Version 1.0 Page 60 of 145

- Screening test for hepatitis B surface antigen (HBsAg) and hepatitis B core antibody (HBcAb; a subject whose HBsAg is negative and HBcAb is positive may be enrolled if a hepatitis B virus [HBV] DNA test is negative and either the subject is treated with potent antiviral therapy or is retested for HBsAg and HBV DNA every month while on study drug treatment).
- Screening tests for human immunodeficiency virus (HIV) and hepatitis C virus (HCV)
- Serum beta human chorionic gonadotropin (β-hCG) pregnancy test for women of childbearing potential or follicle-stimulating hormone (FSH) for postmenopausal women (Section 11.5)
- Urinalysis (Section 11.5)
- Record concomitant medications (Section 9.2)
- Record adverse events (using CTCAE and CRS revised grading system for grading; Section 11.1)
- Pretreatment fresh tumor biopsy (optional; by specific subject consent) to be examined
 by fluorescent immunohistochemical assay for tumor-cell expression of SSTR2 and
 tumor and immune-cell expression of proliferation and exhaustion markers, and by
 Nanostring analysis of nucleic acid and protein content

7.9.1.2. Baseline Assessments (Day -1 or 1)

If a test or assessment is performed on both Day -1 and Day 1, the Day 1 (predose) test is considered the baseline:

- Medical history
- Abbreviated PE (Section 11.7)
- Neurological examination
- ECOG performance status (Appendix B)
- Vital signs (Section 11.8)
- Height, weight
- ECG: standard 12-lead, supine position (Section 11.6)
- CBC (Section 11.5)
- Chemistry panel (Section 11.5)
- Coagulation panel (Section 11.5)
- Urinalysis (Section 11.5)
- Urine β-hCG pregnancy test for women of childbearing potential (Section 11.5)
- Blood for cell surface markers by flow cytometry or other similar bioanalytical methods (Section 13.3)
- Serum for MCPyV assay (Part A and Part B only)

Version 1.0 Page 61 of 145

- PK, cytokine/inflammation panel blood sample (Section 13.1)
- Immunogenicity (ADA) blood sample (Section 13.1)
- Blood for biobanking (Section 13.4)
- Record concomitant medications (Section 9.2) and AEs

7.9.2. Subject Enrollment

Subjects who have completed screening activities and whose eligibility has been confirmed by the Medical Monitor will be considered enrolled in the study.

7.9.3. Treatment Cycle Assessments

The schedule of required procedures and clinical site study days for each cycle are detailed in the Schedule of Assessments (Table 7). The day prior to Cycle 1 Day 1 is Day -1.

Subjects will be followed for PFS and overall survival at 6 and 12 months after end of treatment (EOT) by telephone, email, or mail contact from the clinical site (Section 7.9.5).

Procedures during the treatment cycles to 4 weeks after EOT are detailed in Sections 7.9.3.1 to 7.9.3.2. Study days for required procedures are specified in the Schedule of Assessments (Table 7).

7.9.3.1. Clinical Assessments

PEs and laboratory evaluations may be performed within 24 hours prior to XmAb18087 infusion:

- Record concomitant medications and AEs (CTCAE and CRS revised grading system, Section 11.1).
- Abbreviated, symptom-directed PE, including weight
- ECOG performance status (Appendix B)
- Vital signs (Section 11.8):
 - On infusion days, time points include: within 60 minutes of predose; approximately 15, 30, and 60 minutes after start of infusion (± 5 minutes for each time point); immediately (within 5 minutes) before end of infusion (EOI; if different than 60 minutes from start of infusion); approximately 15, 30, and 60 minutes after EOI (± 5 minutes for each time point); and then hourly (± 5 minutes) for 3 hours. The pulse oximetry for blood oxygen saturation level needs to be captured with each vital sign collection; however, pulse oximetry monitoring must be maintained continuously throughout the entire admission or observation period for each administration of XmAb18087. For information on management of oxygen saturation of 90% or lower, see Section 11.3.3.1.
 - On non-dosing days, vitals should be measured before blood is drawn.
 - For subjects who tolerate 3 XmAb18087 consecutive infusions without an infusion reaction during the infusion or postinfusion observation period and who have completed 4 infusions at the highest dose for that subject, the postinfusion

Version 1.0 Page 62 of 145

observation period and vital signs assessment may be reduced from 4 hours to 2 hours.

